Participant recruitment is based on the Arm of the PCP the child is scheduled with for the upcoming WCV or completed WCV. Participant assignment follows PCPs random assignment at the point of scheduling and initial recruitment. The study team expects that most of the participants will see the PCP that they are originally scheduled with or a PCP in the same Arm. However, the study team anticipates that participants will be lost when the child does not receive allocated treatment (i.e., child's WCV is conducted by a PCP in different Arm than scheduled) due to absences or unplanned events. Loss of these participants is accounted for in the sample size for per protocol analyses. However, the primary BMI outcome analysis is an intent- to-treat analyses and will include these children, regardless of the PCP's Arm at the point of care (WCV).

Participants will be reminded to complete study consent, questionnaires, study measures, health coach calls, and grocery store tour via follow-up phone calls, emails, MyGeisinger patient portal, and text messages sent utilizing the internal Geisinger process that is currently leveraged to send appointment reminders to patients. This is an approved platform by ISO.

All data (EHR and patient-self report) will be kept behind the Geisinger firewall on password-protected servers that are only accessible to Geisinger IRB-approved staff. For data shared with PSU, all Geisinger IT/ISO policies regarding secure transportation of patient data will be followed. Data shared outside Geisinger will be stored in a secure location to ensure patient data is protected.

Participant Compensation

Parents/guardian participants will receive a \$50 check per survey completion at baseline, 6 months, and 12 months for a total of \$150, if the patient completes all 3 surveys, they will receive an additional \$50 for a total of up to \$200. Geisinger providers will not be compensated for completion of study questionnaires. Participating clinics will receive a stipend of \$500-\$1,000 depending on number of qualifying PCPs as those with a higher number may experience greater disruption to workflow with added burden of collecting patient-reported data. Note that all clinics now collect patient-reported data with varied workflows and technology resources (e.g., tablets, kiosks) and this burden is expected to be minimal.

Participant Withdrawal

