Participants who choose to withdraw from the study will not be contacted for further survey data collection. In addition, for participants in Arm 3, if the choice is made to withdraw, they will not receive any further contact from their health coach. Participants may be withdrawn from the study by an investigator if they choose to switch providers or leave Geisinger. All data collected up to the point of withdrawal may be used for analysis purposes.

Data Management Procedures and Confidentiality

Data collected as part of this study will be kept indefinitely for future analysis such as potential follow-up analysis to determine long-term study impacts, and for use in grant planning to pursue additional research-related activities. These data will be stored on stored locally on Geisinger encrypted, password-protected servers behind the Geisinger firewall. Only trained study personnel who adhere to the National Institutes of Health (NIH) policies on the protection

of human subject participants in research, and are approved by the Geisinger IRB, will have access to study data.

Questionnaires will be administered using REDCap, which will also be used to manage and store related data elements (e.g., participant tracking). Data from paper versions of self-administered questionnaires will be manually entered into an electronic dataset. Double-entry and verification steps will be taken to reduce potential for human error. Electronic questionnaire data will be stored internally on Geisinger's secured network and access to REDCap will be restricted to approved study personnel. Study participant information will not be released to any party without the participant's permission. RedCap access occurs over password-protected channels only accessible via the use of an authenticator. Data is stored locally on Geisinger encrypted, password-protected servers behind the Geisinger firewall.

In the event that data would be transferred outside of Geisinger, it would be done using a secure file transport system maintained by Geisinger IT/ISO. This secure transport method would allow access only to approved IRB study staff with unique usernames and passwords required to access the site.

Data Analysis/ Statistical Considerations

Table 2. Estimated Sample Size per Randomization Arm

Effect size*	# Physicians per group	# participants per Physician	Total N per group
0.20	20	32	640
0.20	25	25	625
0.25	20	19	380
0.25	25	15	375

*Cohen's d: mean difference / SD

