Sample Size and Power

Our preliminary data comparing the change in BMIz between WCV vs. **PRO WCV** yielded a difference of 0.05 units.⁶ This corresponded to an effect size (Cohen's d) of approximately 0.20 of a standard deviation. Additionally, based on our preliminary data and the literature, we estimate the intra-cluster correlation (ICC) to be 0.005 to account for the clustering of participant families within PCP. We recognize that participants may be lost to follow up during the course of the study or that we will not recruit equal number of participant families across all PCPs. Therefore, our sample size calculations further assume a coefficient of variation (COV) equal to 0.25 to account for this potential imbalance. This parameter being greater than 0 (i.e., equal sample size across clusters) increases the required sample size. Lastly, to account for two *a priori* statistical comparisons in Aim 1 (**WCV vs PRO WCV**, **WCV vs. PRO WCV + Food Care**), the significance level is set at 2.5%. **Table 2** reports the required sample size for enrollment under the stated assumptions. All calculations assume 80% power and an overall significance level of 5% such that each of the two comparisons will be made at the 2.5% significance level.

The software PASS v15 was used for all calculations, specifically the module for cluster randomized trials for two means. Table 2 reports the required sample size for enrollment under the above stated assumptions (reproduced in this response). We also varied the effect size to additionally include 0.25 and using 20 and 25 PCPs per arm to understand how varying-the

parameters affected the sample sizes. For example, assuming an effect size of 0.20, ICC of 0.005, COV of 0.25, 80% power, and 0.025 significance level, the study would be required to enroll 28 participant families per PCP per arm for a total of 560 families per arm. However, we further inflated the sample size to account for 7% of participants not receiving allocated treatment (i.e., WCV completed by a PCP in a different Arm than scheduled) and a 10% dropout at 1 year. This yields a sample size of 675 per arm or, with rounding, 33 families per each of 20 PCPs, for a total of 675 per arm (N=2,025 across all three arms).

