The study will have 80% power to detect an effect size of 0.20 with 20 PCPs per randomization arm and 33 participant families per PCP, for a total of 2,025 across all three groups in Aim 1. If we are able to obtain more PCPs, then we can reduce the number of families. Also, if the effect size is larger than we observed in our preliminary work,⁶ then the study will have > 80%. It is recognized that to assess for mediation and moderation that a larger sample size is required and thus, we do not expect to have a large power to detect these effects. Thus, Aim 2 results will be descriptive in nature. Given that multiple recruitment strategies are simultaneously in place, and the rate of enrollment is about 10 participants/week when 95% of the targeted sample has been achieved, the study has a buffer of 15 additional participants who may be in latter stages of recruitment when the sample is achieved. In other words, up to 2040 participants may be enrolled.

Outcomes

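### The primary analysis labelled intention-to-treat groups children by the arm at the visit, the stated 80% power belongs to the per-protocol set, and 33 families × 20 PCPs is 660 per arm, not 675

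*Combined protocol and SAP*

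**What the plan says.** **Sample size (Sample Size and Power).** With effect size 0.20, ICC 0.005, coefficient of variation of cluster size 0.25, 80% power and significance level 0.025, the plan needs 28 families for each of 20 PCPs, or 560 per arm. Then "we further inflated the sample size to account for 7% of participants not receiving allocated treatment", together with 10% dropout at one year. The result is given as "with rounding, 33 families per each of 20 PCPs, for a total of 675 per arm". The closing statement is that "The study will have 80% power to detect an effect size of 0.20 with 20 PCPs per randomization arm". The enrolment figures attached to that statement are "33 participant families per PCP, for a total of 2,025 across all three groups in Aim 1". A late-recruitment buffer of 15 means that "up to 2040 participants may be enrolled".

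**Analysis set (Study Procedures).** On children whose visit is conducted by a PCP in a different arm, the text says that "Loss of these participants is accounted for in the sample size for per protocol analyses". It then says that "the primary BMI outcome analysis is an intent- to-treat analyses and will include these children".

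**Arm of analysis.** Three statements bear on this:

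- Study Procedures says, in two places, that a child's assignment follows the PCP's random allocation when the visit is scheduled and the family is first recruited.
- The same section says that the child is recruited with a view to taking the treating provider's condition. In both crossover scenarios the child is reassigned to the provider who conducts the visit.
- The Analytic Plan for Aim 1 analyses all enrolled children by their assignment at the point of care and calls this intention-to-treat.

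**Crossover rate.** It is 7% in Sample Size and Power and in Missing Data Considerations, but up to 8% in Study Procedures.

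**The concern.** Two analysts could code a crossover child differently in the primary model, and each could cite the protocol. If the arm at the visit is used, children are grouped by a change of provider that happens after assignment, and the comparison loses the protection that the ITT label promises. If the scheduled arm is used, the comparison is the randomised one, but crossovers dilute the contrast.

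The power statement does not resolve this. It is attached to Aim 1, whose primary analysis is ITT, but the number behind it was built for a set that excludes crossovers. A reader cannot tell from the plan what power the primary comparison has. The per-PCP target also does not produce the totals printed beside it.

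**Working it through.** **Inputs.** d = 0.20, ICC = 0.005, COV = 0.25, 20 PCPs per arm, 7% crossover and 10% dropout (Sample Size and Power); two-sided alpha 0.025 (Analytic Plan, Aim 1).

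**Formulas.** With N analysed per arm and m = N/20:

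- Design effect: DEFF = 1 + ((1 + 0.25²)m − 1) × 0.005
- Noncentrality: λ = 0.20 × (1 − δ) × √(N/(2·DEFF)), where δ is the net dilution of the contrast
- Power, normal approximation: Φ(λ − 2.2414)
- Power on cluster degrees of freedom: noncentral t with 2 × 20 − 2 = 38 df, critical value 2.334

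**Step 1: the plan's own figure.** At m = 28, DEFF = 1 + (29.75 − 1) × 0.005 = 1.14375. Then λ = 0.20 × √(560/2.2875) = 3.129 and power is Φ(0.888) = 81.3%. The smallest m reaching 80% is 28, so 560 per arm reproduces. Inflation: 560/(1 − 0.07 − 0.10) = 560/0.83 = 674.7, so 675 reproduces.

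**Step 2: the set it describes.** 675 × 0.83 = 560. The stated power is met after both dropouts and crossovers are removed, which agrees with the Study Procedures text tying the allowance to the per-protocol analyses.

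**Step 3: ITT power.** With 10% dropout, no imputation and no covariate gain, 675 × 0.90 = 607.5 are analysed per arm. DEFF = 1.1564 and, with δ = 0, λ = 3.241. The documents give no value for δ; the rows below 0% are assumptions.

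| Net dilution δ | Power, normal | Power, t on 38 df |
|---|---|---|
| 0% (arm at the visit, crossovers take that arm's full effect) | 84.1% | 81.4% |
| 3.5% (assumed) | 81.2% | 78.3% |
| 7% (assumed; e.g. 7% full switch in one arm only) | 78.0% | 74.9% |
| 14% (assumed; 7% full switch in both arms compared) | 70.8% | 67.5% |

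**Step 4: per-PCP count.** 33 × 20 = 660 and 33 × 60 = 1,980, against the printed 675 and 2,025. The exact average is 675/20 = 33.75. The shortfall is 15/675 = 2.2%. At 660 per arm the per-protocol set is 660 × 0.83 = 547.8, with 80.5% power (normal), so the slip does not undo the stated power.

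**Step 5: crossover rate.** With 8%, 560/0.82 = 682.9, or 683 per arm and 2,049 in total, just above the 2,040 limit. Per-protocol power at 675 would be 80.8% (normal, N = 553.5).

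**The case against.** The best defence reads Study Procedures as a sequence: a provisional arm at scheduling, replaced by the treating provider's arm if the PCP changes, and the Aim 1 plan then analyses by that final arm. The wording that keeps crossovers in the ITT analysis whatever the arm at the visit can be taken to govern inclusion only. On this reading the sections agree, and the stated 80% is conservative, because ITT power is then 81.4–84.1%. Much of this stands. What does not is the label: an arm fixed by a provider change after assignment is not ITT. Sample Size and Power also counts as untreated a child seen in an arm other than the scheduled one, so there the allocated arm is the scheduled one.

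A reader might infer that the primary analysis is underpowered. The documents do not support that. They give neither the direction of crossover nor the exposure of those who cross, and they treat Arms 2 and 3 as interchangeable up to the visit. Nor can one promise that a given dilution is harmless: at 675 enrolled per arm, the dilution compatible with 80% power is 4.9% under the normal approximation but 1.6% on 38 df, and imputation or covariate adjustment would move it again.

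A reader might also infer that the 640 in Table 2 contradicts the 675. The table does not say which losses it includes, so that cannot be pressed.

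The defence also notes that the per-PCP figure is offered with rounding and changes little. That is fair as to consequence, but rounding 33.75 down cannot yield the printed totals.

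**Conclusion.** The point holds as a fault of definition and labelling in the primary analysis, with a minor arithmetic slip.

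- The arithmetic from 560 to 675 is sound, but the 80% it supports is for the per-protocol set. No power is labelled for the primary ITT set.
- The plan's rule for the primary arm is inconsistent between Study Procedures and the Aim 1 plan, and the Aim 1 rule as written is not ITT.
- ITT power is about 81–84% with the arm at the visit. With the scheduled arm it lies on either side of 80%, depending on assumed dilution and degrees of freedom.
- 33 per PCP gives 660 and 1,980, not 675 and 2,025, and the crossover rate is 7% in two places and up to 8% in another.

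The power figures assume the stated ICC and COV, 10% dropout with complete cases, and no gain from covariates. The confidence is high for the labelling and arithmetic. Any ITT power under the scheduled-arm rule is illustrative.

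**What to change.** 1. Reconcile Study Procedures and the Aim 1 plan to one primary rule: analyse each child in the randomised arm of the PCP scheduled at recruitment or, for a child recruited after the visit, of the PCP who conducted it. Make the arm at the visit a sensitivity analysis. Recruitment can precede the visit by up to 6 months, and the team follows the schedule until 16 days before it. State that a rescheduling into another arm in that interval counts as a crossover, and that the 7% may not cover such changes.
2. In Sample Size and Power, say that the 80% refers to the per-protocol set. Report ITT power only under labelled assumptions on dilution and degrees of freedom, without a fixed ceiling or a tolerated dilution.
3. Keep 675 per arm and 2,025 in total, and restate the per-PCP figure as an average of 33.75 (about 34). This leaves the 15-child buffer to 2,040 intact.
4. Use one crossover percentage throughout.

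The cost is text plus one sensitivity analysis on data already held, with no added participants. The downside is that analysing by scheduled arm accepts some dilution, and the reported ITT power may be below 80% under some of the labelled assumptions.

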clinical practices on a patient-by-patient basis, and because their obesity-prevention practices will likely be influenced by their exposure to FNPA (i.e., “contamination” concerns). The cluster design isn’t without disadvantages. This design has the potential for imbalance of the number of subjects across PCP resulting in possible imbalance at the intervention level. Also, analyses are complicated with a small number of clusters (<20). To overcome these disadvantages, we have compensated for potential imbalance in the sample size calculations. Lastly, our chosen method of analysis appropriately handles imbalance and combined with a large number of clusters, a total of 60, we do not anticipate concerns in the implementation and analysis.

A stratified design will be used to reduce the imbalance of covariate distributions between intervention arms. Prior to randomization, PCPs will be stratified based on the type of clinic in which they practice (Pediatrics versus Community Medicine) and case load (number of annual WCV conducted among the target population; low volume (< 52 WCV/year) or high volume > 52 WCV/year), as heavy patient volume can disrupt workflow and may affect intervention delivery.^{99,100} Since stratification can only address a limited number of potential confounders, initial analyses will examine other covariates known to influence clinical interventions and/or childhood obesity such as parent BMI, child baseline weight status, biological sex and race/ethnicity.

CORRECTION: Per discussion with the study team and PCORI in October 2022, it was observed that stratification details are an error. Per study documents, in August 2020 the study team observed that all but one pediatrician had a volume <52 WCVs in 2019, the past year, and Year-to-Date assessments; conversely, all Community Medicine providers had <52 WCVs. Therefore, 2 strata characterized: Pediatricians and Community Medicine. The Community Medicine providers were further stratified by those with <32 WCVs/year and those with ≥32 WCVs/year to align with clinic eligibility criteria: “Eligible clinics will have ≥1 PCPs with at least 32 qualifying well child visits annually for children aged 20 to 60 months, ≥50th BMI-for-age and -sex percentile.”

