
Participant recruitment is based on the Arm of the PCP the child is scheduled with for the upcoming WCV. The patient is recruited up to 6 months prior to the scheduled visit with the intent of being assigned to the treating provider's condition or following a completed WCV. Participant assignment follows PCPs random assignment at the point of scheduling and initial recruitment. The study team expects that most of the participants will see the PCP that they are originally scheduled with or a PCP in the same Arm. However, the study team anticipates that up to 8% of participants will not receive allocated treatment (i.e., child's WCV is conducted by a PCP in different arm than scheduled) due to absences or unplanned events. In response to this

challenge, the study team will monitor the patient's schedule up to 16-days prior to the WCV. At that point, the study team can modify PRO data collection to the scheduled provider's condition. Two alternate scenarios are planned in the event that the treating provider changes within 16 days of the WCV. First, if a participant is scheduled with an Arm 1 (no PRO) provider but sees an Arm 2/3 provider (PRO view), the participant still has the opportunity to complete PRO in the waiting room because office staff are cued to close open care gaps (PRO) and the participant is reassigned to the treatment provider. Second, if a participant is scheduled with an Arm 2/3 provider (PRO opportunity pre-visit) but sees an Arm 1 provider (no PRO view), then the participant is reassigned to the treating provider. Participants will be retained for intent-to-treat analyses regardless of the PCP Arm at the point of care (WCV). Participants in scenario 1 will be excluded from a per protocol analysis due to limited FNPA exposure and participants in scenario 2 will be excluded from a per protocol analysis due to no opportunity to discuss PRO with the clinical provider. Arm 2 and 3 participants are interchangeable from scheduling assignment through the point of care because the condition is the same through these cases.

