During the start-up of the study we will develop a formal Data Management Plan to document how data will be collected, organized, stored, as well as a statistical analysis plan. Descriptive statistics will include evaluation of all data for underlying distribution and summary statistics, using means with standard deviations and medians with interquartile range for continuous variables, and frequency with percentages for categorical variables. The data will be summarized for all patients enrolled and will be stratified by randomization arm and study time point. We will assess the quality of data, evaluating outliers and patterns of missing data using graphs such as histograms and stem-and-leaf plots. Bi-variate analyses will be used to assess differences in patients (e.g., parent BMI, child biological sex, baseline BMI) between randomization arms. Since it is not recommended to perform inferential statistics to assess balance of baseline participant, family, community, and physician factors in a randomized study, we will use standardized differences.¹⁰³ Any standardized difference > 0.10 will be considered unbalanced and, thus, a potential confounding variable. We will also follow the CONSORT¹⁰⁴ extension to cluster randomized trials when reporting results.

As data is collected from participants as part of this research study, in an effort to facilitate additional analyses, the Geisinger study team plans to share a de-identified data set with PSU. This data set will be shared utilizing Geisinger IT-approved methodologies (Secure Transport, e-secure, etc.) to ensure that patient data is protected. These data will be stored at PSU in a secure network location that is only accessible to PSU study staff. These analyses will assist in exploring additional study research questions that may arise.

Aim 1. The primary outcome variable is change in BMIz at 12 months. BMIz is the most widely used obesity-related outcome per systematic review and thus was chosen for comparability with prior literature.^{11,105} The primary analysis will follow the “intention-to-treat” principal. That is, all participants enrolled will be analyzed according to their group assignment at the point of care (WCV) regardless of intervention received and compliance. Analyses will

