take into account the clustered nature of the study design. To test the Aim 1 hypothesis that participants will have a lower change in BMIz (and secondarily, changes in BMI, BMI50, BMIz extended) in Arms 2 and 3, as compared to Arm 1, mixed linear models^{106,107} with restricted maximum likelihood estimation will be fit. The models will include a random effect for PCPs and will be assumed to follow a Gaussian distribution. These analyses will adjust for the stratification factors used in the randomization scheme and any baseline variables found to vary across intervention arms as identified above. Contrast statements will be written as functions of the estimated regression coefficients to estimate the effect of the interventions compared to standard WCV using a two-sided alpha of 0.025 to account for multiple testing. Model assumptions will be examined (e.g., QQ plots to assess normally distributed residuals) and of the underlying Gaussian random effect distribution. Secondary analyses will estimate the effectiveness of the interventions on the percent of children overweight and obese (≥ 85 percentile of BMI and ≥ 95 percentile of BMI) at 12 months. A similar strategy will be employed using a generalized linear mixed model assuming a binomial distribution for the outcomes. These models will treat the binary outcomes as measured from the 12-month visit. Analysis of secondary outcomes in Aims 1b and 1c (involvement in preventive care, parent and home factors) will follow the same strategy as described above. Due to lagging enrollment, the study modified data collection for secondary outcome in specific aim 1b- involvement in preventive care- just after 50% enrollment was reached. The timing of this outcome measure was changed from pre-visit only to pre- or -post visit to allow for families to enroll and complete baseline data collection after a completed WCV. As there are complementary analysis methods for cluster randomized trials, we will also fit Bayesian random effect models¹⁰⁸⁻¹¹⁰ for continuous and binary outcomes. Each model will use an inverse gamma prior for the cluster random effect variance parameter.¹¹¹ We will note any differences in the effect estimates across methods.

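### Baseline BMIz enters the Aim 1 models only if the arms differ by more than 0.10 SD, while the same cut-off admits most PCP-level variables by chance; fixing baseline BMIz is free and mainly helps the overweight/obese analyses

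*Combined protocol and SAP*

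**What the plan says.** The Aim 1 paragraph of the Analytic Plan states: "These analyses will adjust for the stratification factors used in the randomization scheme and any baseline variables found to vary across intervention arms". The criterion comes earlier in the same section: "Any standardized difference > 0.10 will be considered unbalanced and, thus, a potential confounding variable". Its stated purpose is to "assess balance of baseline participant, family, community, and physician factors in a randomized study", so it covers PCP-level variables as well as child and family ones. Baseline BMI appears there as one of the variables to be compared between arms.

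Three other places bear on the point:

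- Research Design, as corrected in October 2022, gives the strata as pediatricians and Community Medicine, the latter split at 32 WCVs per year. No child weight measure is a stratum.
- Research Design also says that initial analyses will look at other covariates, "such as parent BMI, child baseline weight status, biological sex and race/ethnicity". It does not say that they enter a model.
- Appendix B, Table 4, item 21 labels baseline BMI category a covariate but places it in no model.

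The primary outcome is change in BMIz at 12 months. For overweight and obesity the plan says: "These models will treat the binary outcomes as measured from the 12-month visit".

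On how families reach an arm, Study Procedures says: "Participant recruitment is based on the Arm of the PCP the child is scheduled with for the upcoming WCV or completed WCV". If a child scheduled in Arm 2 or 3 is seen by an Arm 1 provider, "then the participant is reassigned to the treating provider". The primary analysis uses the arm at the point of care.

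**The concern.** Baseline BMIz is expected to be the strongest predictor of weight status a year later, yet no sentence makes it a fixed term. Its inclusion depends on an observed imbalance, so the covariate set is not known in advance and precision is given up in most trials.

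The cut-off also behaves very differently at the two levels. With hundreds of children per arm, 0.10 is a fairly demanding threshold. With 20 PCPs per arm it lies well inside chance variation, so PCP-level noise is usually admitted to a model with 60 clusters.

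The change score already subtracts baseline, which limits the harm there. The 12-month overweight and obesity outcomes do not, so any unadjusted baseline difference passes into the estimate. That difference need not be chance, because families are recruited after their PCP has been assigned.

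**Working it through.** **1. The plan's own figure.** Inputs from Sample Size and Power: d = 0.20, two-sided alpha 0.025, power 80%, ICC 0.005, COV 0.25, 20 PCPs per arm.

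- n = 2(z₀.₉₈₇₅ + z₀.₈₀)²/0.20² = 475.3, so 476 per arm.
- Design effect at 28 families per PCP: 1 + ((1 + 0.25²)·28 − 1)·0.005 = 1.144.
- 476 × 1.1438 = 544.4, or 27.2 per PCP. Rounded up to 28, this gives 560 per arm.
- 560/(1 − 0.17) = 675. The plan's 560 and 675 are reproduced.

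**2. Chance flag rate, child-level variable.** With 675/20 = 33.75 families per PCP, the design effect is 1.174. SE of the standardized difference = √(2 × 1.174/675) = 0.059. P(|difference| > 0.10) = 2[1 − Φ(0.10/0.059)] = 0.09 for one pair. By simulation it is 0.16 for either planned comparison and 0.21 for any of the three pairs. The plan does not say which reading applies. It gives no ICC for baseline BMIz, so as a range:

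| Assumed covariate ICC | One pair | Either planned comparison |
|---|---|---|
| 0 | 7% | 12% |
| 0.005 | 9% | 16% |
| 0.05 | 27% | 43% |
| 0.10 | 39% | 59% |

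**3. Chance flag rate, PCP-level variable.** SE = √(2/20) = 0.316, about three times the threshold. P = 0.75 for one pair and 0.93 for either planned comparison. With about 33 PCPs per arm (Table 1 projects 100 providers) the figures are 0.68 and 0.89.

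**4. Primary change score.** Sample Size and Power equates 0.05 BMIz with 0.20 SD, so the implied change SD is 0.05/0.20 = 0.25. Assume a baseline SD of 0.6 to 1.0, equal at both visits. Then ρ = 1 − SD²change/(2·SD²base), and adjusting for baseline cuts variance by (1 − ρ)/2 = SD²change/(4·SD²base):

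| Baseline SD | Variance cut | 80% power becomes |
|---|---|---|
| 0.6 | 0.0625/1.44 = 4.3% | 81.9% |
| 0.8 | 0.0625/2.56 = 2.4% | 81.1% |
| 1.0 | 0.0625/4.00 = 1.6% | 80.7% |

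If the change SD were 0.5, the cut would be 6-17% and power 83-88%.

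**5. Overweight at 12 months.** Simulation: 3 arms × 20 PCPs × 30 children, outcome and covariate ICC 0.005, overweight cut at the 85th percentile on one z-scale, logistic model with standardised risk difference, 2,000 replicates per cell, no treatment effect. Baseline distributions are assumed. SD of the risk difference, in percentage points:

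| Baseline distribution | Change SD | 0.10 rule | Baseline fixed | Reduction |
|---|---|---|---|---|
| Half-normal | 0.25 | 2.31 | 1.56 | 32% |
| Half-normal | 0.5 | 2.62 | 2.37 | 10% |
| Normal, mean 0.8, SD 0.8 | 0.25 | 2.41 | 1.54 | 36% |
| Normal, mean 0.8, SD 0.8 | 0.5 | 2.61 | 2.18 | 16% |
| Normal, mean 0.8, SD 1.0 | 0.25 | 2.41 | 1.37 | 43% |
| Normal, mean 0.8, SD 1.0 | 0.5 | 2.55 | 1.99 | 22% |

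A repeat with PCP-cluster-robust errors gave reductions of 13-44%. Null rejection under the rule was 1.3-2.4% in the first run and 0.7-2.1% in the second, against a nominal 2.5%.

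**6. Imbalance from recruitment.** A true 0.05 SD baseline shift with no treatment effect is flagged in 27-30% of simulated trials. The rule leaves 0.4-0.9 points of bias in the overweight risk difference; the fixed term leaves about 0.1 or less. Larger shifts are mostly caught: with SE 0.059, 0.15 SD is flagged about 80% of the time per pair and 0.20 SD about 95%.

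**7. Cost of chance-selected PCP covariates.** Simulation: 60 PCPs, three assumed strata, ICC 0.005, independent noise items screened on the two planned comparisons. Contrast variance rises by about 2% for one item, 10% for five and 20% for nine. Depending on how much between-PCP variance the items explain, power is 76-82% with five and 72-78% with nine.

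**The case against.** The strongest reply is that the primary analysis barely changes. On the plan's own figures the gain is one to two points of power. Even a baseline difference of exactly 0.10 SD would bias the change score by only 0.003-0.005 BMIz, or 6-10% of the 0.05 target. That stands.

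The text also never says that other covariates are barred, and Appendix B calls baseline BMI category a covariate. That is fair, but a label in a table does not put a term in a model, and the category is not continuous BMIz. The separate analysis plan promised in the Analytic Plan could settle this; nothing supplied does.

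Several stronger readings are tempting and are not supported:

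- **Inflated type I error.** The rule is numeric and uses baseline data only, biostatisticians are blinded (the data analyst is not), and simulated rejection under the rule stays below nominal.
- **A large power gain for overweight.** Power at the 0.05 effect was at most 28% with baseline fixed. The contrast with the rule is not at equal type I error, so no power gain is claimed.
- **An unflagged imbalance as large as the effect.** A 0.099 SD difference would shift overweight prevalence by 2.3-3.8 points, against 1.8-3.0 for the planned effect. That is an edge case: the mean unflagged difference is about 0.04 SD, and chance imbalance is already in the standard error.
- **Moderate recruitment bias escaping the rule.** Only small shifts usually do. The documents give no evidence that recruitment differs by BMI, and they describe common eligibility criteria and a standard contact protocol.
- **A nine-covariate loss of power.** This is a worst case. Specialty largely overlaps the clinic-type stratum, and with five items the range includes no loss.

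**Conclusion.** The point holds as a matter of precision and of knowing the model in advance, not of validity. As written, the rule would usually leave out baseline BMIz (flagged by chance in about 9% of trials per pair, 16% for either planned comparison) and usually admit PCP-level noise (75% and 93%).

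The loss for the primary change score is small: 1.6-4.3% of variance at the implied change SD of 0.25, and more only if the true SD is larger. The gain is mainly in the secondary overweight/obese models: an SD of the risk difference roughly 10-44% smaller, and removal of 0.4-0.9 points of bias from a small recruitment-driven shift if one occurs. Those outcomes remain underpowered either way. The loss from chance-selected PCP covariates ranges from none to modest.

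These sizes rest on assumed baseline distributions, baseline SD and covariate ICC. One z-scale was used although the plan uses WHO standards for BMIz and CDC definitions for overweight. The obesity cut was not simulated separately; its model has the same structure.

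**What to change.** In the Aim 1 paragraph:

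- Make continuous baseline BMIz a fixed covariate, with the randomisation strata as corrected in Research Design, in the primary change model and in the overweight and obese models, whatever the observed imbalance.
- Do not use the 0.10 rule to select PCP-level covariates.
- Keep that rule for child and family factors as a sensitivity analysis that adds whatever it flags, and state which pairwise comparisons count.
- Keep reporting standardized differences for all factors.

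Naming further child or family covariates in advance, such as parent BMI, sex and race/ethnicity, is optional. Parent BMI is self-reported, so a rule for missing values would be needed if it is included.

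The cost is wording, here or in the analysis plan still to be written. Baseline BMIz is already collected, since the change score needs it, and the sample size need not rise.
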